Protocol

Randomized Clinical Trial Evaluating the Impact of E-cigarette Device Warnings NCT05714982

7/8/2025

Protocol Synopsis

Study Title	Randomized Clinical Trial Evaluating the Impact of E-cigarette Device Warnings
Funder	National Institute on Drug Abuse (NIDA)
Clinical Phase	N/A
Study Rationale	 The purpose of this randomized clinical trial is to determine whether ecigarette warnings increase intentions to quit vaping without the unintended consequence of pushing users toward smoking. This trial addresses these issues by evaluating the impact of e-cigarette warnings by randomly assigning vapers to have their devices and refills labeled with control messages, text warnings, or pictorial warnings.
Study	This trial will assess the impact of e-cigarette warnings on vapers'
Objective(s)	devices and refills in a randomized clinical trial.
Study Design	Randomized experiment
Subject Population key criteria for and Exclusion:	 Inclusion Criteria Be 21 years or older Currently vape every day or some days Use an e-cigarette that contains nicotine Be able to attend 2 in-person appointments
	 Be able to bring in e-cigarette device and 2 weeks' worth or refills to 2 in-person appointments Be willing to let us apply a sticker to the device and refill materials Be willing to use only the labeled e-cigarette during the study Be able to complete 3 surveys online at home Be able to read and speak English Be able to complete a survey on a computer without help
	 Pregnant people If e-cigarette device cannot be labeled Vapers concurrently enrolled in any research studies about vaping or
	 using other tobacco products Vapers who live in the same household as someone who has enrolled in the study
Number of	~1,200
Subjects	
Study Duration	Each subject's participation will last approximately 4 weeks.
Study Phases	There are two phases: (1) Screening : screening for eligibility and obtaining consent and (2) Intervention : study intervention/experimental treatment.
Efficacy	The primary outcome is vaping quit intentions measured by 3 survey items at 5
Evaluations Statistical and Analytic Plan	time points: post-labeling (Visit 1) and at 1, 2, 3, and 4 weeks (Visits 2-5). • See document titled Statistical Analysis Plan.
Data and Safety Monitoring Plan	 The principal investigator is responsible for data quality management and ongoing assessment of safety.

Study Protocol

This trial will assess the impact of e-cigarette warnings on vapers' devices and refills in a randomized clinical trial.

Recruitment: Vapers will first undergo screening online or call the study center to complete the screening survey over the phone. Trial staff will schedule eligible vapers for 2 in-person visits. For each of the 2 visits, vapers will be asked to bring the vapes and refill materials they plan to use over the next 2 weeks.

Informed Consent: Prior to consenting vapers, trial staff will visually inspect photo identification of vapers to confirm that they are 21 years or older. At the beginning of the first appointment, trial staff will explain the consent form and ask the vaper to read the form. Once the participant has finished reading the form, the trial staff member will ask the participant if he or she has any questions. Then both parties will sign the consent form and the participant will receive a copy of the consent form.

Randomization: At the first visit, trial staff will randomly assign participants to one of the three trial arms by using Qualtrics software. Vapers have an equal chance of being randomized to have labels with control, text, or pictorial warnings.

Assessment: Participants will attend 2 in-person appointments at the study office (at Visit 1 and Visit 3 that are spaced 2 weeks apart). The visits will last about 45-60 minutes. At Visit 1 participants will take a survey, have their vape device and refills labeled based on their trial arm, and take another survey. At Visit 3, participants take a survey and have their vape device and refills labeled based on their trial arm. Participants will also be emailed 3 more surveys to complete online at home (taken at Visit 2, 4, and 5). Thus participants will take 5 weekly surveys overall.

Detailed description of the intervention: At each in-person appointment, participants will bring in the vapes and refills they plan to use over the next 2 weeks for labeling. While participants are taking the survey, trial staff will label the devices and refills based on their trial arm.

Participants randomized to the text warning arm will have labels with information about the health harms of vaping applied to their vapes and refills. Participants randomized to the pictorial arm will have labels with pictorial images and text about the health harms of vaping. Participants assigned to the control arm will have labels with neutral statements about vaping. Each trial arm will have four labels (two labels for Visit 1 and two additional labels for Visit 3). Trial staff will return labeled vapes and refills in a clear plastic bag with the ecigarette warning labels applied to a card. Trial investigators developed the text, images, and design of these labels.

The trial staff will instruct participants in all trial arms to vape or not vape as they normally would. At the end of the trial, participants will receive a link to more information about the risks of vaping and tobacco use.

Statistical analysis plan

Randomized Clinical Trial Evaluating the Impact of E-cigarette Device Warnings

NCT05714982

2/7/2023, Edited 6/24/2024

Hypotheses

This trial evaluates the impact of e-cigarette health warnings by randomly assigning vapers to have their devices and refills labeled with control messages, text warnings, or pictorial warnings.

The primary hypotheses are about the main trial outcome of vaping quit intentions across the 4 weeks of the trial. We hypothesize that text warnings will elicit higher vaping quit intentions than control messages. We also hypothesize that pictorial warnings will elicit higher vaping quit intentions than text warnings.

For secondary outcomes, we hypothesize that text warnings will elicit higher consumer understanding, information seeking and sharing, and vaping behavior change than control messages, and that pictorial warnings will elicit higher scores on these measures than text warnings. We do not have hypotheses about the impact of the warnings on unintended effects.

Analytic plan

Statistical analyses will use two-tailed tests and a critical alpha of .05.

Primary trial outcome

Vaping quit intentions will be measured using a 3-item scale at 5 time points: post-labeling (Visit 1) and at 1, 2, 3, and 4 weeks (Visits 2-5). The 3 items will be averaged to create a composite quit intention score for each time point. The primary trial outcome will be an average vaping quit intentions score across the 5 time points (i.e., grand mean of quit intentions). We will use all available data in computing 1) the quit intention score at each time point and 2) the aggregate quit intention score across time points. Because the quit intention survey items are forced response, missingness will be uncommon, and the use of two layers of averaging will naturally address most missingness. In the unexpected situation of having no intentions data for a participant, we will set their value to the grand mean for the trial overall (ignoring trial arm).

We will estimate a general linear model with quit intentions as the continuous outcome and trial arm as a 3-level categorical, between-subjects predictor (pictorial, text, control; text arm will be the reference group). We will not adjust for demographic or other baseline characteristics per CONSORT recommendations (Consort, 2010). We will examine the following variables measured pre-randomization as potential moderators by adding categorical main effects for these terms and their interaction with trial arm: age, education, income, gender, sexual orientation, race, vaping frequency (some days or every day), and current cigarette smoking status. We will probe statistically significant interactions by examining the effect of trial arm within strata of the moderator, using Bonferroni corrections for the post-hoc tests.

We estimated sample size for a 3 arm trial using the following inputs: 80% power, α set at .05, an effect size Cohen's *d* of .16, number of measurements set at 4.2 time points (estimated average number of completed sessions based on our previous cigarette pack labeling trial; Brewer et al., 2016), and an interclass correlation (ICC) of .7 (based on an observed ICC in that trial; Brewer et al., 2016). The previous effect size estimate is based on the average observed *d* in two online experiments (Brewer et al., 2019; Brewer et al., in prep) between pictorial vs text warnings; control vs. text comparisons were larger in these two experiments.

For descriptive purposes, we will examine mean vaping quit intentions at each trial visit, calculating the mean and standard error. We will compare the trial arms graphically at each time point, examining whether means for each trial arm fall outside of the confidence interval for the other arms.

Secondary trial outcomes

Except as noted below, we will again estimate a general linear model for each secondary outcome shown in Table 1, with trial arm as a 3-level categorical, between-subjects predictor (pictorial, text, control; text arm will be the reference group). We will handle missingness as we did for the primary outcome.

Vaping quit attempt and cigarette smoking quit attempts will each be dichotomous outcomes (any quit attempt during the trial). We will estimate a logistic regression model with quit attempt as the outcome and trial arm as the categorial predictor with text arm as the reference group.

Construct	Variable type, range
Consumer understanding	
Knowledge	Continuous, 0-100%
Cognitive elaboration	Continuous, 1-5
Perceived likelihood of illness from vaping	Continuous, 1-5
Negative affect	Continuous, 1-5
Information seeking and sharing	
Attention to warning	Continuous, 1-5
Information seeking	Continuous, 0-6
Number of conversations in past week	Continuous, 0-100
Vaping behavior change	
Vaping reinforcement attitudes	Continuous, 1-5
Uncontrolled vaping	Continuous, 1-5
Number of times forgoing a vape in past week	Continuous, 0-6 times
Made vaping quit attempt (for 24 hours) in past 4 weeks	Dichotomous, 0 or 1
Successful quitting of vaping (at last survey)	Dichotomous, 0 or 1
Unintended effects	
Inaccurate risk perception	Continuous, 0% to 100%
Stigma	Continuous, 1-5
Smoking quit intentions among dual users	Continuous, 1-5
Made smoking quit attempt (for 24 hours) in past 4 weeks among dual users	Dichotomous, 0 or 1

Table 1. Secondary outcomes

Edit 6/24/2024: In Table 1, changed range of values for information seeking from "Continuous, 1-5" to "Continuous, 0-6". Changed range of values for number of conversations in past week from "Continuous, 1-5" to "Continuous, 0-100". These updates align this document with the main trial registry.

References

Brewer, N. T., Queen, T., Sheldon, J. M., Lazard, A. J., Ribisl, K. M., Ebrahimi Kalan, M., & Hall, M. G. (In preparation). Impact of e-cigarette warnings on perceived message effectiveness.

- Brewer, N. T., Jeong, M., Hall, M. G., Baig, S. A., Mendel, J. R., Lazard, A. J., ... & Ribisl, K. M. (2019). Impact of e-cigarette health warnings on motivation to vape and smoke. *Tobacco Control*, *28*, e64-e70.
- Brewer, N. T., Hall, M. G., Noar, S. M., Parada, H., Stein-Seroussi, A., Bach, L. E., ... & Ribisl, K.
 M. (2016). Effect of pictorial cigarette pack warnings on changes in smoking behavior: A randomized clinical trial. *JAMA Internal Medicine*, *176*, 905-912.

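### Optional and low priority: adjusting the primary linear model for vaping frequency and smoking status, both recorded before randomization, could narrow its confidence intervals slightly at almost no cost

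*SAP*

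**What the plan says.** The SAP (Analytic plan, Primary trial outcome) defines the primary outcome as each participant's average quit-intention score over five time points. The model is: "We will estimate a general linear model with quit intentions as the continuous outcome and trial arm as a 3-level categorical, between-subjects predictor", with text as the reference arm. It then states: "We will not adjust for demographic or other baseline characteristics per CONSORT recommendations".

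The same paragraph continues: "We will examine the following variables measured pre-randomization as potential moderators". The list ends with "vaping frequency (some days or every day), and current cigarette smoking status". Each moderator is examined by "adding categorical main effects for these terms and their interaction with trial arm". So the SAP itself treats these two variables as baseline data and already plans to put them in models of the primary outcome, but not in the model that gives the primary arm comparison. Vaping every day or some days is also an inclusion criterion in the protocol synopsis.

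The secondary outcomes follow the primary model: "Except as noted below, we will again estimate a general linear model for each secondary outcome shown in Table 1". For quit attempts the SAP changes method: "We will estimate a logistic regression model with quit attempt as the outcome".

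**The concern.** In a linear model of a randomized comparison, a baseline variable that predicts the outcome removes residual variance. Adjusting for it leaves the target mean difference unchanged and narrows its interval at the same sample size. The plan forgoes this for two variables it says it will hold.

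Precision is most useful for pictorial versus text. That contrast is one of the two primary hypotheses, and the SAP's sample size paragraph bases its effect size on it, noting that control-versus-text differences were larger. What is at stake is a slightly wider interval than necessary. Validity is not at stake. The moderator models do not supply the missing precision, because they contain arm-by-moderator interactions and are not the source of the primary estimate.

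**Working it through.** **Inputs.** From the SAP: d = .16, 4.2 measurements, ICC .7, two-sided α of .05, 80% power. From the protocol: about 1,200 participants with equal allocation, taken as 400 per arm. R² is an assumption, because neither document relates these covariates to quit intentions. The calculations also assume that d is expressed in single-occasion SDs, which the SAP does not state.

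**Variance of the averaged score**, in single-occasion units: (1 + 3.2 × .7)/4.2 = .7714.

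**The plan's own figure.** The SAP introduces its inputs with "We estimated sample size for a 3 arm trial using the following inputs: 80% power" but names no test. With an omnibus F test on 2 df and f = d/2 = .08, f²/.7714 gives a required N of 1,167, close to the protocol's figure. Power at 1,200 is 81.3%. A two-sided pictorial-versus-text contrast on the same inputs needs 474 per arm, or 1,422 in total.

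**Effect of adjustment.** Pairwise SE = √(2 × .7714 × (1 − R²)/400), half-width = 1.96 × SE, and power = Φ(.16/SE − 1.96). At R² = 0, SE = .0621, .16/SE = 2.576, and power = Φ(.616) = 73.1%. Omnibus power uses f² = .0064/(.7714 × (1 − R²)).

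| Assumed R² | SE | 95% half-width (SD) | Interval narrower by | Pairwise power | Omnibus power | Equivalent N = 1,200/(1 − R²) |
|---|---|---|---|---|---|---|
| 0 | .0621 | .1217 | 0 | 73.1% | 81.3% | 1,200 |
| 1% | .0618 | .1211 | 0.5% | 73.5% | 81.7% | 1,212 |
| 2% | .0615 | .1205 | 1.0% | 74.0% | 82.1% | 1,224 |
| 5% | .0605 | .1186 | 2.5% | 75.3% | 83.3% | 1,263 |

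An R² of 10% would give an interval 5.1% narrower and pairwise power of 77.5%. Reaching 80% pairwise power at 400 per arm would need R² of about 15.4%.

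**Scale for R².** Take one binary covariate split 50/50, whose groups differ by δ single-occasion SDs. With b = .25 × δ²/.7714, R² = b/(1 + b). For δ = 0.2, b = .0130 and R² is 1.3%. For δ = 0.3, b = .0292 and R² is 2.8%. With an 80/20 split, .16 replaces .25 and R² falls to 0.8% and 1.8%. These differences are illustrations and do not come from the documents.

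**Cost if the covariates predict nothing.** The SE grows by a factor of about √(1196/(1196 − k)) for k extra terms: 1.0008 for k = 2 and 1.0013 for k = 3. A simulation of 4,000 trials with two non-prognostic binary covariates gave a mean ratio of 1.0008. Pairwise power becomes 73.0% and omnibus power 81.2%. Adjustment breaks even at R² = k/1196, which is 0.17% or 0.25%. Net of the cost with k = 2, pairwise power is 73.9% at R² of 2% and 75.2% at 5%.

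**Sensitivity to the scale of d.** If d refers instead to the SD of the averaged score, SE = √(2/400) = .0707, and unadjusted pairwise power is Φ(.16/.0707 − 1.96), about 62%. The percentage narrowing of the interval is the same on either reading.

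**The case against.** The strongest objection is that this is a preference. The unadjusted comparison is valid, was chosen deliberately and is stated with a reason. The cited recommendation is not reproduced in the documents, so it cannot be assessed here. The benefit depends on an R² that the documents do not give. At 2%, the half-width moves only from .1217 to .1205 SD, which would rarely change a conclusion. All of this stands, and it is why the point is optional.

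A second objection is that a careless edit would make a clear plan less clear. The moderator models are built on the primary model, so those for age, education, income and the rest could appear to inherit the two covariates. The word *again* in the secondary-outcome section could carry the change over as well. Deleting the no-adjustment sentence would also remove the only statement that demographics stay out. This stands too, and the amendment has to settle each of these matters.

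In favour of the change, the trade is uneven: the worst case is about 0.1% of the standard error, and break-even lies at R² below 0.3%.

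Two stronger readings may tempt a reader:

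- One might infer from 73.1% that the trial misses its stated 80%. The documents do not support this. The SAP names no test, its inputs read as an omnibus test give 81.3% at 1,200, and the scale of d is not stated. Nor would adjustment bring the pairwise contrast to 80% at any R² in the table.
- One might expect a larger gain from adjusting for baseline quit intentions, since the protocol describes a survey before labeling at Visit 1. The documents do not say that this survey measures quit intentions, so no such gain is claimed.

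**Conclusion.** The point holds as a low-priority, optional improvement. The primary model omits two variables that the SAP describes as measured before randomization and already uses elsewhere. Adjusting for them would keep the same target mean difference. It would narrow the interval by about 0.5% to 2.5% if they explain 1% to 5% of the variance of the averaged score. The gain could be nil, and the cost in that case is about 0.1% of the standard error. These percentages do not depend on the scale of d; the power figures do. It would be wrong to conclude that the unadjusted analysis is biased or that the SAP is in error.

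**What to change.** If outcomes have not been examined by arm, replace the no-adjustment sentence in a dated SAP amendment:

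> The primary linear model will contain trial arm, vaping frequency (two levels) and current smoking status, as recorded before randomization. No other baseline variable, demographic or otherwise, will be adjusted for. The unadjusted model will be reported as a sensitivity analysis. Moderator models will contain only trial arm, the moderator and their interaction. Secondary-outcome models will contain trial arm only.

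State the smoking-status categories, and keep any participant with a missing covariate in the model, for example under a separate missing category. Secondary models should stay as they are for two reasons: smoking status may be constant or nearly so among dual users, and adjusting a logistic model changes the odds ratio being estimated.

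If outcomes have been examined by arm, keep the unadjusted model as primary and report the adjusted model as a sensitivity analysis only. The SAP is dated 2/7/2023 and was edited 6/24/2024, and the protocol is dated 7/8/2025. Neither says whether outcomes have been examined by arm, so the sponsor should confirm this first. Changing the primary model after that would cost credibility.

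The cost is the amendment and two or three model terms, with no new data collection.

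### Age is tested as a moderator in unstated categories; if age is recorded in years, a continuous age-by-arm interaction is a cheap improvement

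*SAP*

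**What the plan says.** The SAP, under the primary trial outcome, plans to look at eight pre-randomization variables as "potential moderators by adding categorical main effects for these terms and their interaction with trial arm: age, education, income, gender, sexual orientation, race", followed by vaping frequency and smoking status. Every one of them enters as a categorical term. Significant interactions are followed up by estimating the arm effect separately in each stratum, with a Bonferroni correction, which confirms that age is to be grouped.

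Levels are spelled out only for vaping frequency. For age, education and income the SAP gives no levels, no cut points, and no continuous or trend alternative. It states no moderator hypothesis and no power for these tests. The general rule is: "Statistical analyses will use two-tailed tests and a critical alpha of .05".

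**The concern.** Age is a quantity. A grouped analysis treats everyone in a band as the same age, so any gradient inside the band is lost. With three arms, each age group beyond the second also adds 2 df to the interaction test. And because the cut points are not written down, they could be settled after the data are in hand, and the answer for age would depend on them.

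At stake is whether the trial would notice that the labels work differently in younger and older vapers, and whether a reported age finding, positive or negative, could be defended as pre-planned.

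**Working it through.** **Inputs from the documents.** About 1,200 participants (Protocol synopsis); "Vapers have an equal chance of being randomized to have labels with control, text, or pictorial warnings", so about 400 per arm; alpha .05 two-sided. The SAP's sample-size inputs are "80% power, α set at .05", "an effect size Cohen's *d* of .16", "number of measurements set at 4.2 time points" and "an interclass correlation (ICC) of .7".

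**Assumed, because the documents are silent.** Age recorded in years; roughly linear moderation; 2 to 5 equal-size age groups; age normal, uniform, or right-skewed as 21 + gamma(shape 2, scale 8).

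**Step 1: the plan's own figure.** Averaging 4.2 measurements gives a variance factor of (1 + 3.2 × 0.7)/4.2 = 0.771. A three-arm omnibus F test with f = d/2 = 0.08 has noncentrality 1,200 × 0.08² / 0.771 = 9.96 and power 81%; 80% needs about 1,165. So about 1,200 is reproduced under that reading, which the SAP does not name. (A single pairwise contrast at 400 per arm has about 73%; that is a separate matter.) These inputs concern the arm effect. Nothing in them sizes the moderator tests.

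**Step 2: method.** Power = P[F′(df1, df2, λ) > F(.95; df1, df2)]. The linear age-by-arm test has df1 = 2 and df2 = 1,194; 80% power needs λ = 9.66. With k groups, df1 = 2(k − 1), df2 = 1,200 − 3k, and λ is multiplied by the share of age variance lying between groups. For uniform age that share is 1 − 1/k²; for normal age and k = 2 it is 2/π = .637.

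**Step 3: age, when the linear test has 80% power.**

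| Groups | df1 | Normal: share, power | Uniform: share, power | Skewed: share, power |
|---|---|---|---|---|
| 2 | 2 | .637, 59% | .750, 67% | .553, 53% |
| 3 | 4 | .793, 58% | .889, 64% | .716, 53% |
| 4 | 6 | .861, 55% | .938, 59% | .794, 51% |
| 5 | 8 | .897, 51% | .960, 55% | .838, 48% |

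Example: normal age, quartiles: λ = 9.66 × .861 = 8.31 on 6 df gives 55%. With two groups no df are added, so the whole loss is lost information.

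**Step 4: dependence on the cut.** Take the skewed distribution (mean 21 + 16, variance 128) and one cut. For share p below the cut, with mean m above 21, the share kept is p/(1 − p) × (m − 16)²/128.
- Cut at 30: p = .310, m = 5.40, kept .395, λ = 3.81, power 40%.
- Cut at 40: p = .686, m = 9.88, kept .639, λ = 6.17, power 60%.

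The same data and the same gradient give 20 points' difference from the choice of cut alone.

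**Step 5: a weaker gradient.** The planning effect on the grand-mean scale is 0.16/√0.771 = 0.182 SD. If only the pictorial-text difference changes, by half of that (0.091) per SD of age, the linear test has λ = 2.21 and about 25% power. At 25%, two to five groups have about 13% to 20%. The loss is 5.4 to 12.4 points, rounded outwards to 5 to 13. If both contrasts change by 0.091 per SD, λ = 6.64 and linear power is 63%; normal age in 2 to 5 groups then has 44% to 35%.

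**Step 6: education and income.** With k ordered levels and an exactly linear gradient, λ is unchanged but df1 is 2(k − 1). Against 80% for the trend, the factor test has 70%, 62%, 57% and 52% for k = 3, 4, 5 and 6, a loss of 10 to 28 points. Reverse the case: let the effect be a step at the top of k equal-size levels and give the factor test 80%. The trend test keeps .75, .60 and .50 of λ for k = 3, 4 and 5 and has 77%, 73% and 69%. For a symmetric U shape it has 5%, its false-positive rate.

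**The case against.** The best defense is that categorical coding is a legitimate choice when no shape is predicted. The SAP calls these variables potential moderators and states no direction; a factor can pick up any pattern between levels, while a linear term looks mainly for a gradient. It also fits the planned stratum-by-stratum follow-up. For education and income this stands: step 6 shows that swapping the factor for a score is a trade-off, and equal spacing of the scores is an assumption of its own. It stands less well for age, where the bands are undefined and the recommended spline shows any curvature, although a sensitivity analysis does not restore power to the main interaction test.

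A second objection is that the loss cannot be sized from the documents. That also stands. A reader might infer that categorical coding simply costs this trial 10 to 30 points of power for age, education and income. The documents do not support that as a flat statement. It needs near-linear moderation, mid-range power for the linear test and about 3 to 6 levels, none of which is given. If the interaction tests are weak to begin with, the loss in points is smaller and neither coding would usually find the gradient. For education or income with only two levels there is no df penalty. Nor does the SAP say that the categories are unordered; that is only the usual meaning of a categorical term in a general linear model.

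**Conclusion.** The point holds for age, as an inexpensive improvement rather than a flaw in the trial's main result. The SAP commits to grouping age without defining the groups, and a continuous term is the better method if age is recorded in years. Under linear moderation that a 2-df test would detect with 80% power, two to five equal-size groups lower power to 51-59% (normal age), 55-67% (uniform) or 48-53% (skewed); at 25% linear power the loss is about 5 to 13 points. The size is conditional throughout. The dependence on cut points does not rest on any one power figure.

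Two further inferences are not supported. The plan is not wrong to treat education and income as factors. And nothing in the documents shows that age cut points were or will be picked from the results; they are merely unstated. The primary three-arm model and both primary hypotheses are untouched.

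**What to change.** If age is recorded in years, amend the moderator paragraph so that age enters as a continuous main effect with a continuous-age-by-arm interaction (2 df). Add a 3-knot spline as a sensitivity analysis, with the knot rule stated. In place of post-hoc age strata, report model-based arm effects with confidence intervals at pre-specified ages (for example 25, 35 and 50). If age is collected only in bands, or the sponsor prefers groups, write the bands into the SAP.

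Keep education and income as categorical factors and state their levels. A 2-df ordered-trend interaction may be added for each, labeled supplementary.

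The cost is SAP wording and minor code, with no new data. The small downside is that a linear age term can miss a non-monotone pattern, which the spline is there to show. The amendment should be dated before any moderator result is seen; otherwise the continuous-age analysis should be labeled post hoc.

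### A significant arm-by-moderator interaction is followed up only within strata, which does not show which arm contrast, or which strata, differ

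*SAP*

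**What the plan says.** The SAP's Hypotheses section has two separate primary hypotheses: text above control, and pictorial above text. Under Primary trial outcome, the model has arm as a three-level factor with text as reference. Eight pre-randomization variables are examined as moderators by "adding categorical main effects for these terms and their interaction with trial arm". The follow-up is one sentence: "We will probe statistically significant interactions by examining the effect of trial arm within strata of the moderator, using Bonferroni corrections". The general rule is "Statistical analyses will use two-tailed tests and a critical alpha of .05".

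So heterogeneity is tested first, and probing happens only if that test is significant. No step compares a given arm contrast between strata. The SAP does not give the number of tests in the Bonferroni family, the category boundaries of the moderators, or any adjustment across the eight interaction tests.

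**The concern.** A three-arm interaction pools two contrasts. With two strata it has 2 degrees of freedom; with k strata, 2(k-1). Significance says that something differs, not which hypothesis is moderated or where. The planned follow-up asks another question: is each arm effect different from zero inside each stratum? An effect that is the same in two strata can easily reach significance in one and miss it in the other.

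At stake is the subgroup message. A reader could conclude that text warnings work in daily vapers and not in some-day vapers, when only the pictorial-text contrast differs between those groups.

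**Working it through.** **Inputs from the documents.** About 1,200 participants (Protocol Synopsis, Number of Subjects). Equal allocation (Protocol, Randomization: "Vapers have an equal chance of being randomized to have labels with control, text, or pictorial warnings"), so about 400 per arm. Two-sided alpha .05. Sample-size inputs from the SAP: "80% power, α set at .05", "an effect size Cohen's *d* of .16", "number of measurements set at 4.2 time points" and "an interclass correlation (ICC) of .7".

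**The plan's own figure.** The SAP gives these inputs but no N. An omnibus three-arm F test with f = d/2 = .08 and noncentrality f² × N × m / (1 + (m-1) × ICC) needs N = 1,167 (.0064 × 1,167 × 4.2 / 3.24 = 9.68), within 3% of 1,200. On the averaged score the variance factor is (1 + 3.2 × .7)/4.2 = .771, so d becomes .16/√.771 = .182.

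**Assumptions not in the documents.** Two strata, split 70/30 or 50/50; SD 1 on the averaged score; text-control effect δ equal in both strata, at .10, .182, .25 or .40; pictorial-text truly moderated (.30 versus -.05); Bonferroni over 4 tests (2 strata × 2 contrasts), so .05/4 = .0125 and critical z = 2.498.

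**Step 1: power inside strata, before the interaction gate.** Power ≈ Φ(δ/SE - 2.498), with SE = √(2/n) and n per arm within the stratum.
- 70/30: n = 280 and 120, SE = .0845 and .1291. At δ = .25, power is Φ(.460) = .68 and Φ(-.562) = .29. The chance that exactly one is significant is .677 × .713 + .323 × .287 = .58.
- 50/50: n = 200, SE = .100. At δ = .25, power is Φ(.002) = .50 in each, and the chance is 2 × .50 × .50 = .50.

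**Step 2: given a significant interaction** (simulation, 200,000 trials per scenario).

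| Equal text-control effect (SD) | Power, 70% / 30% stratum | Exactly one significant, no gate, 50/50 | Same, no gate, 70/30 | Same, given significant interaction, 70/30 |
|---|---|---|---|---|
| .10 | 9% / 4% | 13% | 13% | 15% |
| .182 | 37% / 14% | 38% | 40% | 43% |
| .25 | 68% / 29% | 50% | 58% | 59% |
| .40 | 99% / 73% | 13% | 28% | 30% |

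At 50/50 and .25 SD, the figure given a significant interaction is 53%. Testing the between-strata difference in text minus control directly at unadjusted .05 wrongly declares a difference in about 7% of the same trials.

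**Step 3: other scenarios.**
- Three strata split 60/25/15, pictorial-text equal (.25) in the two larger strata and -.25 in the third, text-control .25 throughout: the probe splits the two larger strata in 58%, the direct contrast in 7%.
- Text-control moderated (.5 versus 0), pictorial-text equal: at .182 SD the equal contrast is split in 38% (50/50), 41% (70/30) and 44% (80/20); at .30 SD in 43%, 55% and 68%. The direct contrast at .025 errs in 2.5-3%.

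**Step 4: no arm effect differs.** The gate opens in 5% of trials. With both effects at .182 SD, an open gate together with any split contrast occurs in 4.3-4.8% of trials per moderator. Over eight unadjusted moderators, the chance that at least one gate opens is up to 1 - .95⁸ = 33.7% if they are independent.

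**The case against.** The strongest reply is that the interaction test is itself the test of whether arm effects differ between strata, and the SAP puts it first. That stands. A reader might infer that the plan has no test of effect modification, or that it will often report differences where none exist. Step 4 shows otherwise: at most about 5% of trials per moderator.

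A reader might also blame unequal strata. The split is already 50% before the gate, and 53% after it, with equal strata at .25 SD. Limited within-stratum power is the main driver there, and imbalance adds to it. Only at .40 SD does imbalance make the larger contribution (13% to 28% before the gate).

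Third, the SAP says only that it will examine arm effects within strata. It does not say that significance in one stratum alone will be reported as a difference, and nothing bars reporting the interaction coefficients. That is correct. The criticism is that the stated follow-up cannot answer the question raised, not that the SAP commits to a wrong conclusion.

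Fourth, the rates depend on assumed effects and splits and are conditional on a significant interaction. Unconditionally, the 59% is 38%.

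Finally, the direct contrast has a price. In the 70/30, .25 SD scenario, given a significant interaction, the truly moderated contrast looks split under the planned probe in 90% of trials. A Holm-adjusted direct contrast detects it in 76%, and in 22% no contrast is declared. The 90% is not the power of a test of difference, so the two are not like for like, but the cost is real.

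**Conclusion.** The point holds in limited form. After a significant interaction, the planned within-stratum tests do not show which contrast or which strata differ. Where one contrast is truly moderated, the other appears significant in one stratum only in about 15-59% of trials with a significant interaction (70/30 split, N 1,200, text-control effect .10 to .40 SD, Bonferroni over 4 tests), against about 7% wrongly declared by a direct contrast at .05. Splits, effects and family size are assumptions.

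The documents do not support the stronger reading that equal effects will often be called different because strata differ in size. The moderator analyses carry no stated hypotheses and the primary comparisons are untouched, so this is a minor improvement.

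**What to change.** Replace the probing sentence with wording to this effect: *After a significant arm-by-moderator interaction, we will estimate with 95% CIs the difference between strata in (a) text minus control and (b) pictorial minus text, adjusting for multiplicity within the moderator. Only these contrasts will support a statement that an effect differs by subgroup. Within-stratum arm effects will be shown with CIs as description.* State the number of tests in each adjusted family.

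Optional and minor: use Holm in place of Bonferroni for any within-stratum tests kept. Bonferroni is valid. In the 70/30, .25 SD scenario, Holm raises detection of the true text-control effect from 67% to 73% in the larger stratum and from about 30% to about 37% in the smaller, but Holm gives no simple simultaneous intervals.

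The cost is SAP wording. With text as reference, the model already contains these interaction coefficients; moderators with more than two levels also need linear combinations of them. Fewer subgroup statements will be made, and sometimes none despite a significant interaction.
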